4 CONCOMITANT MEDICATIONS/MEASURES

Medications or vaccinations specifically prohibited in the exclusion criteria are not allowed during the ongoing trial. If there is a clinical indication for one of these or other medications or vaccinations specifically prohibited during the trial, discontinuation from trial therapy or vaccination may be required.

For premedication and supportive care measures, see Section [3.4.3.1](#), [3.4.3.2](#) and [3.4.3.3](#).

4.1 ACCEPTABLE MEDICATIONS

All treatments that the investigator considers necessary for a subject's welfare may be administered at the discretion of the investigator in keeping with the community standards of medical care. All concomitant medication will be recorded on the case report form (CRF) including all prescription, over-the-counter (OTC), herbal supplements, and IV medications. If changes occur during the trial period, documentation of drug dosage, frequency, route, and date may also be included on the CRF.

All concomitant medications received within 28 days before the first dose of trial treatment and 30 days after the last dose of trial treatment should be recorded.

4.2 CONCOMITANT MEDICATIONS TO BE USED WITH CAUTION

Concomitant medications that fall into the categories below could potentially lead to adverse reactions and should be considered cautionary (except where noted). If a potential study patient is taking any of the medications in the categories described below, the investigator must assess and document the use of medications known or suspected to fall in the following medication categories:

- Growth factors: initiation of G-CSF support (e.g. filgrastim or pegfilgrastim) will be administered at the discretion of the investigator for instances of G2 or higher neutropenia or as prophylaxis to prevent neutropenia. If short-acting G-CSF is initiated (e.g., filgrastim), dosing should continue daily until the patient completes their day 14 study therapy AND the neutrophil count > 5000 cells/ μ L. Alternatively, patients may receive

long-acting G-CSF (e.g., pegfilgrastim) at the discretion of the investigator. Once G-CSF (filgrastim or pegfilgrastim) has been initiated during a previous cycle, the patient should receive prophylactic G-CSF support during all subsequent cycles of therapy. Short-acting G-CSF (e.g., filgrastim) should be given daily starting on day 3 (+/-1 day) and should continue until the patient completes their day 14 study therapy AND the neutrophil count > 5000 cells/ μ L. Alternatively, patients may receive prophylaxis with long-acting G-CSF (e.g., pegfilgrastim) administered on day 3 (+/-1 day) of each cycle at the discretion of the investigator.

- Romidepsin concomitantly with warfarin: Monitor PT and INR more frequently in patients concurrently receiving romidepsin and warfarin. It is not known if there is an interaction with co-administration of lenalidomide and warfarin. Close monitoring of PT and INR is recommended.
- Digoxin: For subjects taking digoxin, periodic monitoring of digoxin plasma levels is recommended due to increased C_{max} and AUC with concomitant lenalidomide therapy (please see prescribing information).
- Erythropoietin stimulating agents or estrogen containing therapies: Subjects taking concomitant therapies such as erythropoietin stimulating agents or estrogen containing therapies, may have an increased risk of venous thromboembolism (please see prescribing information).
- CYP3A4 inhibitors: After the DLT evaluation window, subjects who need to start treatment with strong CYP3A4 inhibitors ([Appendix C](#)), should be monitored closely for toxicities. These are prohibited during the DLT window.

4.3 PROHIBITED MEDICATIONS

Patients are prohibited from receiving the following therapies during treatment on this trial:

- Other therapy for the disease under study not specified in this protocol, unless specifically noted as permitted
- Investigational agents other than lenalidomide, romidepsin and CC-486 (5-azacitidine)
- Rifampin and other strong CYP3A4 inducers ([Appendix C](#))
- Agents that may cause QTc prolongation ([Appendix E](#))
- Radiation therapy

NOTE: Radiation therapy to a symptomatic solitary lesion may be allowed at the investigator's discretion.

- Live vaccines within 30 days prior to the first dose of trial treatment and while participating in the trial. Examples of live vaccines include, but are not limited to, the following: measles, mumps, rubella, varicella/zoster, yellow fever, rabies, BCG, typhoid vaccine and FluMist.

A list of common CYP3A inhibitors or inducers is provided in [Appendix C](#); a comprehensive list of inhibitors, inducers, and substrates may be found at:

<http://medicine.iupui.edu/clipharm/ddis/table.aspx>.

This website is continually revised and should be checked frequently for updates.

Patients who, in the assessment by the investigator, require the use of any of the aforementioned treatments for clinical management should be removed from the study treatment. Patients may receive other medications that the investigator deems to be medically necessary.

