6.3 RESPONSE CRITERIA

6.3.1 Response Assessments

Tumor response will be assessed by the investigator using the RECIL 2017 criteria [66] for all patients with T-cell lymphoma other than CTCL. Global Response Score [67], and modified severity weighted assessment tool (mSWAT) [68] will be used for patients with CTCL. For leukemic disease, leukemic cells (ATL, Sezary or T-PLL) as percentage of PBMCs will also be assessed and reported separately and response will be assessed using consensus guideline [69]. Patient will be re-evaluated for response as outlined in the Study Calendar, Section 3.9.

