6.3.1.1 Response Criteria for PTCL

RECIL 2017 criteria [66] use the Deauville five-point scale for assessment of response via FDG-PET. The five-point scale (5-PS) has been validated for use at interim staging and at the end of treatment and was adopted as the preferred reporting method at the First International Workshop on PET in Lymphoma in Deauville, France (i.e., Deauville criteria), and in several international trials.

The 5-PS PS scores the most intense uptake in a site of initial disease:

1. if present, as follows: no uptake or no residual uptake (when used at interim)
2. slight uptake, but below blood pool (mediastinum)
3. uptake above mediastinal, but below or equal to uptake in the liver
4. uptake slightly to moderately higher than liver
5. markedly increased uptake or any new lesion (on response evaluation)

The sum of longest diameter (SLD) is used for assessment of tumor burden. In patients with disseminated disease, a maximum of three target lesions should be selected and used to estimate tumor response. Target lesions should be selected from those with the largest size that can be reproducibly measured and preferably representing multiple sites and/organs. In most cases, lymph nodes can be considered target lesions if the lymph node longest diameter measures ≥ 15 mm. A lymph node measuring between 10 and 14 mm is considered abnormal but should not be selected as a target lesion. Lymph nodes measuring < 10 mm in diameter are considered normal. In certain anatomical sites (inguinal, axillary, and portocaval), normal lymph nodes may exist in a narrow, elongated form, and such nodes should not be selected as target lesions if alternatives are available. Extranodal lesions are selected as target lesions if they have soft tissue component, based on their

size, and the ease of reproducibility of repeated measurements, with a minimum measurement of the longest diameter of ≥ 15 mm. All other lesions should be identified as nontarget lesions and should be recorded at baseline, without the need to measure them. Nontarget lesions should be followed and reported as present, absent, or clear progression.

Table 86: Response categories based on assessment of target lesions

% Change in sum of diameters of target lesions from nadir					
	CR	PR	MR	SD	PD

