% change from baseline	
 Complete disappearance of all target lesions and all nodes with long axis <10 mm $\geq 30\%$ decrease in the sum of longest diameters of target lesions (PR) with normalization of FDG-PET 	
 $\geq 30\%$ decrease in the sum of longest diameters of target lesions but not a CR 	
 $\geq 10\%$ decrease in the sum of longest diameters of target lesions but not a PR ($<30\%$) 	
 $<10\%$ decrease or $\leq 20\%$ increase in the sum of longest diameters of target lesions 	
 $>20\%$ increase in the sum of longest diameters of target lesions For small lymph nodes measuring <15 mm post therapy, a minimum absolute increase of 5 mm and the long diameter should exceed 15 mm Appearance of a new lesion
FDG-PET	Normalization of FDG-PET (Deauville score 1-3)	Positive (Deauville score 4-5)	Any	Any	Any
Bone marrow involvement	Not involved	Any	Any	Any	Any
New lesions	No	No	No	No	Yes or No

CR, complete response; CT, computerized tomography; FDG-PET, [¹⁸F]2-fluoro-2-deoxy-D-glucose; MR, minor response; PD, progression of disease; PR, partial response; SD, stable disease.

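### Radiation to a symptomatic solitary lesion is allowed on treatment, but the written response rules never leave out an irradiated target lesion, so its shrinkage can be scored as drug response

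*Combined protocol and SAP*

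**What the plan says.** Section 4.3 lists radiation among the therapies prohibited during treatment, then adds a NOTE: "Radiation therapy to a symptomatic solitary lesion may be allowed at the investigator's discretion". *Solitary* is not defined, and the target or non-target status of the lesion is not mentioned. The section ends by saying that patients who, in the investigator's assessment, "require the use of any of the aforementioned treatments for clinical management should be removed from the study treatment". It does not say whether the NOTE is an exception to that sentence.

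Section 6.3.1 states: "Tumor response will be assessed by the investigator using the RECIL 2017 criteria" (for T-cell lymphoma other than CTCL). Under 6.3.1.1, in disseminated disease "a maximum of three target lesions should be selected and used to estimate tumor response". The response table carries the heading "Change in sum of diameters of target lesions from nadir" and sets:

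- PR at a decrease of at least 30% in the sum, with PET still positive and no new lesion;
- PD at an increase of more than 20% in the sum, or "Appearance of a new lesion";
- CR at disappearance of all target lesions, or a decrease of at least 30% with a normalized PET; either way with uninvolved marrow and no new lesion.

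Outside the target sum, "Nontarget lesions should be followed and reported as present, absent, or clear progression".

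Best response runs from the start of treatment to progression (6.3.2). EFS counts alternative anti-lymphoma therapy as an event (6.3.4); PFS does not (6.3.5). Section 10.3.2 excludes nobody from the response-evaluable set for radiation. Section 10.4.3 asks for a response report on all eligible patients and censors at last follow-up. None of these sections mentions radiation.

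**The concern.** ORR, CR rate, DOR, PFS and EFS are meant to describe the antitumor activity of the drug combination (1.1.2). Local radiation can shrink a lesion by itself. With at most three target lesions, one lesion can carry a large share of the sum, so under the written rules a local radiation effect enters the drug response directly. The trial is open label, and the investigator who may allow the radiation also scores the response. The confirmatory scan four weeks after a first response (Study Calendar, note 3) shows whether shrinkage persists, not what caused it.

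**Working it through.** The plan gives no figure on this point to reproduce. The check applies its PR and PD cut-offs to assumed lesion sizes, with and without the irradiated lesion.

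**Inputs.** PR at a decrease of at least 30%, PD at an increase of more than 20%, at most three targets (6.3.1.1); 9 patients at the MTD and a maximum of 30 enrolled (10.2); Agresti-Coull intervals (10.4.1). Assumed: targets of 40, 30 and 30 mm (sum 100 mm), the 40 mm lesion irradiated, and baseline still the nadir at the scan in question. Let *w* be the irradiated lesion's share of the baseline sum and *s* its fractional shrinkage.

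**1. Only lesion (w = 1).** A single 40 mm target falling to 20 mm is -50%, which meets PR on size. If PET also normalizes, marrow is uninvolved and no new lesion appears, the CR row is met. With the lesion left out, no target remains to score.

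**2. One lesion among several: PR.** With the others unchanged, PR on size needs w × s ≥ 0.30, so s ≥ 0.30 / w.

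| Share w | Shrinkage needed |
|---|---|
| 50% | 60% |
| 40% | 75% |
| one third | 90% |
| 30% | 100% |

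Below a 30% share the lesion cannot reach PR alone. In the example, clearance gives 60/100 = -40% (PR on size); left out, 60/60 = 0% (SD). The remaining disease would supply the positive PET that the PR row expects.

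**3. One lesion among several: masked growth.** The others can grow by up to (0.20 + w × s) / (1 - w) before the sum rule calls PD.

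- w = 0.40, s = 0.5: 0.40 / 0.60 = 67% (60 to 100 mm; the total is 120, or +20%, SD).
- w = 0.40, s = 1: 0.60 / 0.60 = 100% (60 to 120 mm).
- w = one third: 55% when halved, 80% when cleared.

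A milder case: the 40 mm lesion halves and the others grow 25%. The sum is 20 + 75 = 95, or -5% (SD); left out, 75/60 = +25% (PD).

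**4. Later progression.** Once the sum has fallen to 60, PD needs growth of more than 0.20 × 60 = 12 mm. Had the lesion stayed at 40 mm, it would need more than 0.20 × 100 = 20 mm. The effect on PFS therefore has no fixed direction.

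**5. Effect on ORR of one reclassified patient** (counts are illustrative).

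- 30 patients: 1/30 = 3.3 points, for example 12/30 = 40.0% (95% CI 24.6 to 57.7) to 13/30 = 43.3% (27.4 to 60.8).
- 9 patients at the MTD: 1/9 = 11.1 points, for example 3/9 = 33.3% (11.7 to 64.9) to 4/9 = 44.4% (18.8 to 73.4).

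Both shifts are small beside the interval widths.

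**The case against.** **The adopted criteria may already cover it.** Section 6.3.1 adopts RECIL 2017 by citation and 6.3.1.1 may restate only part of it. The source cannot be checked here, so a reader should not infer that RECIL is silent. What stands is that this protocol writes out its lesion rules in detail and has none for an irradiated lesion.

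**Other sections restrict the permission.** Section 3.4.2 bars other therapies intended to treat the malignancy, the closing sentence of 4.3 can be read as taking such patients off treatment, and 3.8.2 and 3.8.3 change follow-up once a new anti-cancer therapy starts. With the word *symptomatic*, these suggest a narrow palliative exception. They leave the patient's status unclear, but none takes the lesion out of the response calculation, and best response runs to progression, not to the end of treatment.

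**Masking depends on *solitary*.** This stands. If the word means the only lesion, there are no other targets to mask, and steps 2 and 3 fall away. Step 1 remains.

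**CTCL is closed.** This also largely stands. CTCL is excluded by 2.1.1.1 and, for the expansion cohort, by 2.1.2.4, and escalation closed before the 12/07/2022 amendment. A reader might infer a continuing gap in skin scoring with open-ended durations. For CTCL the point is essentially retrospective scoring of patients already enrolled, and 6.3.1.2 already uses the off-treatment date for TTP and DOR.

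**The effect is small and hypothetical.** Lesion sizes are assumed and use is not quantified. This bears on weight, not on whether the rule is needed.

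**Conclusion.** The point holds in a limited form. As written, the rules count radiation shrinkage of a target lesion as response to the drugs. With a sole lesion, this can give PR, or CR under the conditions in step 1. With several lesions, it can give PR on size from a 30% share upward, or hide growth of the other targets.

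Three stronger readings are not supported. Progression in general is not hidden, because new lesions and clear non-target progression still count. Radiation to one lesion cannot by itself produce CR while other disease remains, because CR also needs a normalized PET and uninvolved marrow. The trial's main conclusions are not at risk: the MTD and AE endpoints do not use response, and no test or stopping rule depends on it.

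The effect falls on descriptive secondary endpoints, mainly ORR and also DOR, PFS and EFS. It rests on the irradiated lesion being a target lesion and on the permission being used, which may be rare. The change is still worth making because it is cheap.

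**What to change.** Keep the permission. In 6.3, state that:

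- from the radiation date, an irradiated lesion (or skin area, for mSWAT) is left out of the baseline, nadir and follow-up sums and of the PET score;
- a response first recorded after radiation counts only if non-irradiated disease meets the criterion against its own baseline;
- if no other assessable disease remains, best response is the last post-baseline assessment before radiation; if there is none, the patient is not evaluable for response and counts as a non-responder in the all-eligible-patients analysis.

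All three sums must be reset. If the lesion is dropped from follow-up only, the others growing 25% read as 75 against 100 (-25%) instead of 75 against 60 (+25%, PD).

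State in 4.3 whether the NOTE overrides the closing removal sentence, and in 6.3.4 whether this radiation is an EFS event. List irradiated patients in the report; a separate sensitivity analysis is optional.

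**Cost.** A few sentences and a field for radiation date and site, with no extra scans. The rule can be applied to scans already taken if date and site are on record. The downside is that an occasional genuine drug response in an irradiated lesion is not counted. The last pre-radiation imaging may also be old: about 2 × 28 = 56 days between scheduled scans, or about 28 + 28 + 21 = 77 days before the first on-study scan (baseline up to 28 days before dosing, then Cycle 2 Day 21), and longer with permitted cycle delays.

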5 CORRELATIVE STUDIES FOR RESEARCH

5.1 BIOSPECIMEN COLLECTION

5.1.1 Summary

This study will test the feasibility of concomitant NFκ-B inhibition with lenalidomide and epigenetic modification with CC-486 (5-azacitidine) and romidepsin in patients with T-cell malignancies. Although increased efficacy with the combination has been demonstrated *in vitro*, effects of the combined treatment on the tumor microenvironment, circulating immune cell subsets, cytokine production, and exosome composition are not known. The correlative studies performed in this trial will focus on how lenalidomide alone and in combination affects tumor cells, immune cell subsets, and cytokines in tumor tissue and peripheral blood, and whether these may represent a predictive or prognostic biomarker in patients with TCMs.

Composition of the tumor microenvironment will be analyzed via immunohistochemistry, flow cytometry, and single-cell RNAseq before treatment, after 7 days of single-agent lenalidomide, and after 15 days of combined treatment with lenalidomide, romidepsin, and CC-486 (5-azacitidine). Differences in circulating immune cell subsets associated with administration will be followed throughout treatment to both study the effects of combined therapy on the immune system, and to identify potential biomarkers that would be predictive of response. Circulating tumor DNA and exosome composition will be followed and analyzed with the same goal in mind. Germline DNA will be sequenced to distinguish circulating tumor DNA from other cell-free DNA.

Sample	Collection Details*	Time Points [†]							Supervising Laboratory/ Investigator [^]
		Baseline ⁴ (C1 D-7)	C1 D1	C1 D10	C1 D15	C2-6 D1	C2-6 D10	Follow-up [#]	
Blood Samples									
Lymphocyte subset testing	• 2 x 10mL K ₂ EDTA (lavender-top) tubes	X	X	X	(X)		(X)	(X) ¹	DLM
PBMC banking	• 3 x 10mL Na-heparin (green-top) tube	X	X	X	(X)	X	(X)	X	Leidos CSL
Circulating tumor DNA, plasma banking**	• 1 x 10mL K ₂ EDTA tube • 1 x 10mL Streck/BCT tube	X	X			X		X ²	Leidos CSL
Tissue Samples									
Tissue immune cell subsets	• Two core biopsy samples in RPMI 1640 with 10% human serum and antibiotics • One core biopsy sample in formalin NOTE: Samples may be tumor tissue or bone marrow aspirate/biopsy	X***	(X)		(X)			(X) At disease progression	(RPMI 1640 and DLM/ NCI LP (formalin))

Sample	Collection Details*	Time Points [†]							Supervising Laboratory/ Investigator [^]
		Baseline ⁴ (C1 D-7)	C1 D1	C1 D10	C1 D15	C2-6 D1	C2-6 D10	Follow-up [#]	
Other Samples									
Germline DNA	• Blood, Buccal Swab, or Saliva (preferred) – see 5.4	X							Leidos CSL
(X) = Optional; samples will be collected if adequate time/staff available for processing, and if research blood drawn is less than the allowed limit noted in Section 5.1.3 . If an optional sample is not collected at baseline, it would also not be collected in follow-up unless specifically requested by the PI.									
[†] The location of specimen processing or analysis may be adjusted with the permission of the PI or laboratory investigator.									
*Tubes/media may be adjusted at the time of collection based upon materials available or to ensure the best samples are collected for planned analyses.									
** May be omitted if research blood drawn would be over the allowed limit noted in Section 5.1.3 .									
*** Tumor biopsy (bone marrow, skin, or ultrasound-guided LN biopsies) is required if archival tissue is not available or adequate; otherwise, this is optional									
[†] All time points during treatment are ± 3 days. All follow-up time points are ± 7 days.									
#Subjects who discontinue treatment for a reason other than disease progression and who do not start new treatment should continue to have study bloods collected at the scheduled time points.									
¹ At the end of treatment only.									
² At each follow-up visit prior to disease progression, as specified in Section 3.8.2 .									
⁴ With the exception of tissue immune cell subset (if applicable) and Germline DNA which are to be collected during Baseline, samples correlating to the lead-in window will no longer be collected as the lead-in window has been retired.									

5.1.2 Sample Collection and Processing

5.1.3 Summary

The planned sample collection will be done as specified below and analyses described below may be done on leftover and/or shared sample portions from the respective laboratories, as needed. In addition to the prospectively collected samples below, leftover portions of samples sent for routine laboratory testing (e.g., plasma from CBC/hematologies) may also be retrieved for research tests prior to being discarded. The planned prospective analyses are identified below; laboratories may share resources or collaborate on analyses, if appropriate.

Portions of all samples may be banked for future research analyses; prospective consent will be obtained during the informed consent process.

Tissue samples will also be sent to the Hematopathology Section of the National Cancer Institute Laboratory of Pathology, by courier service.

5.2 BLOOD SAMPLES

All blood samples will be drawn by NIH Clinical Center phlebotomy, inpatient unit, outpatient clinic, or day hospital staff.

5.2.1 Lymphocyte subset testing by flow cytometry (FACS)

- Collect blood in EDTA tubes; gently invert tubes 8-10 times immediately after collection

- Labels listing the patient's name, date of birth, date and time of the blood draw will be affixed to all the tubes by the staff person who obtained the samples.
- Lymphoid Malignancies Branch Clinical Research personnel will arrange for these samples to be delivered to: Immunology Lab, NIH Clinical Center [name]. If the Immunology Section Laboratory is unable to perform these analyses (Lymphocyte Subset Testing-CTCL for patients with cutaneous T-cell lymphoma and Lymphocyte Subset Testing-antiTAC for all other patients) on the specified days, this assessment maybe omitted or replaced with standard TBNK panel

